Prospective Validation Study of a Antiretroviral Therapy (ARV) Decision Support Tool

NCT04080765

July 1, 2019

1. Abstract

The Centers for Disease Control and Prevention (CDC) estimate that 1.2 million people currently live with HIV in the United States; however, less than half have been prescribed antiretroviral (ARV) therapy and are virally suppressed [1,2,3]. ARV regimens generally include multiple drugs from various mechanistic classes. There are currently over 25 ARV drugs approved by the U.S. Food and Drug Administration (FDA), leading to a wide array of potential ARV combinations [4,5].

Treatment of HIV with antiretroviral drugs (ARV) requires complex medical decision-making that incorporates multiple individual patient variables. The existing guidelines provided by the Department of Health and Human Services (DHHS) provide excellent recommendations on choosing initial ARV regimens, but they are dense, cumbersome to navigate, especially for inexperienced providers and for patients with significant co-morbidities or drug resistance mutations [4]. This is particularly problematic given that recent studies have shown a large proportion of HIV care is being provided by primary care practitioners, who may not have received specific training in HIV care.[6] There is thus a need for innovation to improve provider knowledge of HIV evidence based practice recommendations and emerging scientific data, and to assist clinicians in decision making when selecting an appropriate ARV regimen.

Faculty at Johns Hopkins have recently created HIV-ASSIST (<https://www.hivassist.com/>) an online interactive patient-based tool that allows for delivery of tailored educational content that may assist providers to learn HIV treatment principles and support decision making on ARV usage.

Our study design involves a randomized trial of trainees from the Johns Hopkins School of Medicine (SOM) and Residents from Johns Hopkins Medical Institutions, comparing ARV selection for ten hypothetical cases among trainees that have access to the current DHHS guidelines versus trainees that have access to HIV-ASSIST. Our hypothesis is that there will be a statistically significant higher percentage of appropriate ART selection (comparing to a reference standard of HIV experts) in the group using HIV-ASSIST compared to the group using DHHS guidelines alone.

We have previously constructed ten standardized case scenarios in an electronic survey format, and ascertained ARV prescribing preferences from experienced HIV clinicians to serve as the reference standard, to define ‘appropriate ART selection’. We will enroll student and resident trainees from Johns Hopkins, who will be randomized to a control group (with access to current DHHS guidelines) or an intervention group (with access to HIV-ASSIST and current guidelines). We will deliver the same ten case scenarios via electronic survey to study participants, who will be asked to recommend ARV regimens for each case. We will report the percent concordance to the reference standard (i.e percent appropriate ART selection), comparing the intervention group to the control group.

2. Objectives

- a) Primary: To determine the difference in percent concordance (with reference standard; i.e. percent appropriate ART selection) between the group using the DHHS guidelines for ARV selection and the group using HIVASSIST for ARV selection.
- b) Secondary: To determine the difference in time for ARV selection for standardized case scenarios between trainees using HIVASSIST and those using the DHHS guidelines.

3. Background

The Centers for Disease Control and Prevention (CDC) estimate that 1.2 million people currently live with HIV in the United States; however, only less than half have been prescribed antiretroviral (ARV) therapy and are virally suppressed. ARV regimens generally include multiple drugs from various mechanistic classes. There are currently over 30 ARV drugs in 7 different classes that have been approved by the U.S. Food and Drug Administration (FDA), leading to a wide array of potential ARV combinations.

Choosing these drugs is a complex medical decision, and current guidelines advocate individualized therapy that accounts for multiple patient characteristics. Factors that must be considered include: previous ARV treatment, adherence, HIV resistance mutations, viral load, comorbidities (e.g., renal function, cardiovascular disease), and drug interactions. Synthesizing each of these modifying factors is necessary, but complex and time consuming for providers. Challenges in prescribing ARV regimens in a primary care setting become increasingly relevant as HIV continues to become a manageable chronic illness. Recent studies have shown that a large proportion of HIV care is provided by primary care practitioners, and often infectious disease specialists feel uncomfortable managing patient's comorbidities like hypertension and diabetes. With the growing need for increasing involvement of primary care physicians in HIV care management, there is also a growing need to develop tools that allow more effective and efficient learning of HIV treatment principles and that support ARV decision making.

To solve this problem, faculty at Johns Hopkins have created HIV-ASSIST, an online interactive patient-based tool that allows for individualized treatment recommendations through the synthesis of patient-specific factors with existing guidelines and evidence. HIV-ASSIST offers efficient real-time learning of treatment principles and augmented decision support for care providers by delivering informational material about the evidence behind suggested regimens during the use of the tool.

Our goal is to evaluate the impact of using HIV-ASSIST compared to DHHS guidelines in making ARV selections (for both ARV naïve and experienced patients) among trainees that are not experts in HIV care. We have previously ascertained ARV preferences for 10 case scenarios from HIV experts to serve as the reference standard. We will the proportion of ARV selections that are concordant with the reference standard (% appropriate ART selection) between a group of trainees using DHHS guidelines, and a group of trainees using HIVASSIST as well as the guidelines

3. Study Procedures

- a. Study design: Randomized trial of students and trainees to assess the impact of HIVASSIST utilization on ARV selection for standardized case scenarios compared to usage of DHHS guidelines alone.
- b. Study participants and settings: We will enroll up to 200 participants. Students in the Johns Hopkins University SOM or SON (Baltimore, Maryland), and/or internal medicine residents at Johns Hopkins Hospital will be eligible to participate. Participants will be invited to participate via an email to class or program listservs or via flyers posted in the school of medicine or nursing buildings. Individuals that are interested will have a link to a Qualtrics survey where they will receive additional study details.
- c. Enrollment/Randomization: An email will describe the study and will contain a link to the survey; the email will also inform them that their participation is completely voluntary, and that their decision to participate (or not) will in no way affect their academic standing. They will also be informed that no information about individual results/surveys will be shared with their school administration. All participants enrolling in the study will be offered an incentive of \$50 gift card or equivalent; they will receive a link to this gift card via email after their participation. Study enrollment will take place over 12 months. Participants will be recruited on a rolling basis throughout the study period.
 - Qualtrics will be used to deliver the survey, including an initial page explaining the study and asking for consent.
 - Qualtrics will automatically randomize participants to different groups as a part of the survey process, using Qualtrics internal random sequence generator. We do not include any stratifications for randomization as limited demographic detail is collected. The participants were not blinded to their allocation, as they were told which decision-support aids they would have available.
 - The survey will be conducted in one session, and the time to complete the survey will be captured. Individuals not completing the survey in one session will be excluded.
- d. Data collection/Survey:
 - Development of standardized case scenarios: We have previously designed 10 clinical case scenarios for a range of patient situations, including a) ARV naïve b) ARV experienced, suppressed or c) ARV experienced, failing patients (with and without mutations, comorbidities, and common co-medications). In a prior prospective survey, we have ascertained ARV preferences for each case scenario among a cohort of experienced HIV clinicians. These ARV choices for each case scenario will be considered a reference standard to judge acceptability of ARV selections in the study cohort in this study.
 - We will collect basic demographic details of study participant including degree program (NP,MD), level of training (M1, M2), and level of experience with HIV care.
 - Each survey will have its own video tutorial briefly explaining how to use the DHHS guidelines and/or HIV-ASSIST. A link to the video will be provided in the survey. The control group will have a link to the DHHS guidelines in the survey. The experimental group will have a link to both the DHHS guidelines, and the HIVASSIST tool. Each participant must acknowledge that they have successfully accessed their respective resources to help inform their ARV regimen selections. A question at the beginning of both surveys will restrict the participants from

advancing until they have filled information from either DHHS guidelines or HIV-ASSIST correctly. This will be a test of the participant's understanding of how to use the survey and the respective regimen selection aid.

- Study participants will be guided through a survey in which the ten standardized case scenarios (vignettes with relevant HIV and patient variables are provided) are presented, and participants will be asked to propose their ARV treatment regimens. The participant's ARV choices will be recorded. Through Qualtrics software, we will also record the time needed to complete the study.

e. Statistical considerations:

Definitions of appropriate ART selection:

Current DHHS guidelines recommend an individualized approach to ARV selection based on multiple considerations. Several regimens are listed as acceptable for ARV-naïve patients as 'regimens recommended for most people living with HIV', with specific instructions on comorbidities or drug interactions that may lead to selection from a list of 'regimens recommended in some clinical scenarios'. For ARV-experienced patients, the guidelines outline a list of general treatment principles to consider, such as including "at least two, and preferably three, fully active agents."

For each case-scenario in the survey, we have previously collected ARV selections from a cohort of experienced HIV clinicians, recognizing that there may be multiple reasonable ARV regimen options for each case scenario. The ARV choices from the prior survey will be used as the reference standard.

Each question will be graded as 'concordant/appropriate' if the ARV regimens selected by the respondent matches an ARV regimen of any HIV expert, or is consistent with current DHHS guidelines (e.g., selection from the list of "regimens recommended for most people living with HIV" for treatment-naïve case-scenarios; regimens which "include at least two, and preferably three, fully active agents")

Our primary outcome is the proportion of appropriate ARV selection for standardized case scenarios, comparing between trainees and expert HIV clinicians and/or DHHS guidelines. Specifically, we will assess:

- a) The difference in percent appropriate/concordant between the control group, and the intervention group that has access to HIV-ASSIST

Hypothesis: There will be a statistically significant higher percent concordance in the group using HIV-ASSIST compared to the group using DHHS guidelines alone.

Our secondary outcome will look at the time required for each group to reach a correct answer. Specifically, we will assess:

b) The difference in time to ARV selection for standardized case scenarios between trainees using HIV-ASSIST and those using the DHHS guidelines.

Hypothesis: There will be a statistically significant lower time to correct ARV selection in the group using HIV-ASSIST compared to the group using DHHS guidelines.

Sample Size:

There is limited a priori data to estimate the likely percent concordance between trainees/students and HIV experts. We assumed that those participants using DHHS guidelines alone (control) will have an average of up to 50% appropriate responses, with a wide standard deviation of up to 0.5. We anticipate that there will be approximately 80% appropriate ART selections with a standard deviation of 0.1 among those in the intervention arm. With this assumption, we would need 18 individuals in each arm to be adequately powered to detect a difference (two-sided alpha, 0.05). Table 1 shows needed sample size to have 80% power to detect a difference between the control and intervention arms under varying assumptions. In secondary analysis, we will compare the control and intervention arms, stratified by level of training.

DHHS MEAN % APPROPRIATE RESPONSES	0.3	0.3	0.3	0.5	0.5	0.5	0.3	0.3	0.3	0.5	0.5	0.5
HIVASSIST MEAN % APPROPRIATE RESPONSES	0.7	0.7	0.7	0.7	0.7	0.7	0.8	0.8	0.8	0.8	0.8	0.8
DHHS SD	0.1	0.3	0.5	0.1	0.3	0.5	0.1	0.3	0.5	0.1	0.3	0.5
HIVASSIST SD	0.1	0.1	0.1	0.1	0.1	0.1	0.1	0.1	0.1	0.1	0.1	0.1
Sample size needed per group for 80% power	1	4	11	4	16	41	1	1	7	2	7	18

Table 1. Sample Size Variations by Expected Group Means and Standard Deviations

4. Drugs/ Substances/ Devices

a. N/A

5. Risks

a. This study only involves a survey with standardized cases to ascertain clinician preferences for a variety of HIV case scenarios. Participants may feel insecure regarding their self-perceived lack of knowledge regarding HIV management. However, all responses to the survey will be visible only to the study members. There are no other biological risks identified.

- b. Steps taken to minimize the risks.: Participants will be permitted to stop participating in the survey at any time.
- c. Plan for reporting unanticipated problems or study deviations: Participants will be instructed to contact the PI if any problems occur during survey completions. Such problems will be reported to the IRB immediately.
- d. Financial risks to the participants: There are no financial risks to participants.

6. Benefits: Once the data are compiled, analyzed, and published, the participants will learn about their collective understanding of HIV antiretroviral management. In addition, the results of this study will allow us to improve HIV-ASSIST, a tool that will greatly expand providers' ability to provide guideline-recommended HIV care. This is particularly important in places where there may not be dedicated HIV training (such as other countries) and in places where there are no HIV providers/a provider with no formal training in HIV care is managing a handful of patients with HIV (which occurs in many rural parts of the United States). Managing HIV in an optimal way not only provides a benefit to patients, it benefits society by reducing patients' viral loads and thus reducing transmission to other persons.

7. Payment and Remuneration

- Participants who complete the study will receive a link through email for an electronic \$50 Amazon gift card. There will be no penalties for not completing the study.

8. Costs and Funding

- The only cost of the study is the Amazon incentives that we will offer our participants to complete the study. These costs will be paid using internal Johns Hopkins Institute of Educational Excellence Berkheimer Grant, awarded to [name] (PI).

9. Trial Registration: clinicaltrials.gov

10. Roles and Responsibilities: The study was designed by [name] (PI) and [name] (Co-investigator), who also led protocol development, obtained IRB approval, conducted the study, and led analysis and manuscript writing. The funders had no role in the design, collection, management, analysis or interpretation of data or writing of the report.

11. The study received approval by the Ethics/IRB committee of Johns Hopkins University

Protocol References

1. CDC. HIV in the United States: At A Glance.
<https://www.cdc.gov/hiv/statistics/overview/ataglance.html> [Accessed March 2018].
2. Foundation KF. The HIV/AIDS Epidemic in the United States: The Basics.

<https://www.kff.org/hivaids/fact-sheet/the-hivaids-epidemic-in-the-united-states-the-basics/>. [Accessed May 2017].

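### A must-pass question on the allocated aid sits between randomisation and case 1, so the trainees compared may be selected differently by arm, and time spent on it enters the recorded survey time.

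*Combined protocol and SAP*

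**What the plan says.** In the combined protocol and SAP, section 3.c (Enrollment/Randomization) places allocation inside the survey: "Qualtrics will automatically randomize participants to different groups as a part of the survey process". Section 3.d then describes arm-specific material: "Each survey will have its own video tutorial briefly explaining how to use the DHHS guidelines and/or HIV-ASSIST". For controls, "The control group will have a link to the DHHS guidelines in the survey"; the intervention arm has links to both the guidelines and HIV-ASSIST.

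Section 3.d goes on to put a question first in each arm's survey, which keeps trainees from "advancing until they have filled information from either DHHS guidelines or HIV-ASSIST correctly". Its purpose is given as "This will be a test of the participant's understanding of how to use the survey and the respective regimen selection aid". The ten cases follow.

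Three other provisions bear on this:

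- 3.c drops anyone who does not finish in a single sitting.
- Section 5 (Risks) lets participants stop whenever they wish and tells them to contact the investigator about problems.
- Section 7 (Payment and Remuneration) ties the gift card to completion.

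On timing, 3.c and 3.d record the time taken for the survey or study as a whole. Sections 2 and 3.e define the secondary outcome as the time to choose a regimen for the case scenarios. No timer for individual cases is described.

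**The concern.** Randomisation makes the two groups comparable at allocation. A later step that decides who supplies outcome data, and whose content depends on the arm, can undo that. Here the step tests skill with the aid, which is plausibly related to how well a trainee would choose regimens with it. If the share who never pass differs by arm, the comparison is between trainees shown to be able to use their aid, screened by tests that may differ in difficulty. It is no longer between trainees given access to one aid or the other.

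The secondary outcome has a problem that needs no dropout. Even if everyone eventually passes, reading, looking up and retrying at the check all run on the recorded clock, and may take longer in one arm.

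**Working it through.** **Step 1: order of events.** The plan does not set the order out as one sequence, but it follows from the text. Allocation takes place in the survey (3.c). Each arm has its own survey and tutorial (3.d). The check stands at the start of each survey and tests "understanding of how to use the survey and the respective regimen selection aid", so it must follow allocation. The cases come after it. A trainee who stops at the check has no case answers and has not completed, so 3.c removes that trainee. Nothing in the documents limits attempts, provides a bypass, requires counts by arm, or says how such trainees enter the primary outcome.

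**Step 2: effect on the primary difference.** The plan has no figure for failures at the check. Its only usable figures are the planning means in 3.e (Sample Size): 80% and 50%, a difference of 80 − 50 = 30 points. Let μ be an arm's mean over everyone randomised, p the share who never pass, and d the amount by which they would score below those who pass, whose mean is m. Then

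μ = (1 − p)m + p(m − d), so m = μ + p·d.

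The bias in the observed difference is d(p_I − p_C), with I for intervention and C for control. The values of d and p below are assumptions. With d = 20 points:

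| Blocked, control | Blocked, intervention | Control mean | Intervention mean | Difference |
|---|---|---|---|---|
| 15% | 5% | 50 + 3 = 53 | 80 + 1 = 81 | 28 |
| 30% | 5% | 50 + 6 = 56 | 80 + 1 = 81 | 25 |
| 5% | 15% | 50 + 1 = 51 | 80 + 3 = 83 | 32 |
| 5% | 30% | 50 + 1 = 51 | 80 + 6 = 86 | 35 |

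Under this model, equal shares give no bias.

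**Step 3: a severe case with no true effect.** Assume both arms have mean 0.5 and SD 0.3 (an SD used in Table 1), normal scores, and 100 per arm (the cap of 200 split equally). Suppose the lowest-scoring fraction f is lost from one arm only. That arm's mean rises by SD × φ(z_f)/(1 − f), where φ is the standard normal density and z_f the normal quantile at f. The two-sided 5% rejection rate comes from 4,000 simulated trials.

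| f | Shift in mean | Rejection rate |
|---|---|---|
| 0 | 0 | about 5% |
| 5% | 0.033 | about 14% |
| 10% | 0.058 | about 31% |
| 20% | 0.105 | about 71% |

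This is a worst case: failure at the check is taken to track case performance perfectly and to occur in one arm alone.

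**Step 4: how far a sensitivity analysis could move.** Suppose those who pass score 80% and 50%, and those without answers count as 0%. The difference is 80(1 − p_I) − 50(1 − p_C):

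- 10% lost in each arm: 72 − 45 = 27
- 10% lost in intervention only: 72 − 50 = 22
- 10% lost in control only: 80 − 45 = 35
- 20% lost in intervention only: 64 − 50 = 14
- 20% lost in control only: 80 − 40 = 40

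**Step 5: timing.** Recorded time = time before case 1 (including the check) + time on the cases. The difference between arms in recorded time is therefore the difference in case time plus the difference in time before case 1. Only the first of these is the secondary outcome.

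**The case against.** The strongest reply is that this is a retry step, not a disqualification. Trainees get a tutorial and a direct link to the aid, may try again without a stated limit, can contact the investigator, and are paid on completion. Medical or nursing students and residents looking up one item may nearly all pass. A check that people can open and use their aid is also sensible where the objectives speak of groups using each aid. All of this stands, and it is why the loss may be small or zero.

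The overlap with the one-session exclusion also stands in part: that rule removes the blocked trainees from the analysis. What the check adds is a cause of loss that depends on the arm, and the absence of any case answer.

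Three stronger readings are tempting, and the documents do not support them:

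- *Blocked trainees are lost beyond recovery.* Their case answers are unobserved, but they were randomised, so they can be counted by arm and scored under a stated rule.
- *The control test is the harder one, so the benefit of HIV-ASSIST is understated.* The Abstract says of the guidelines that "they are dense, cumbersome to navigate, especially for inexperienced providers", but that remark concerns choosing regimens, not one look-up after a tutorial. The question itself is not shown, and the word either leaves unclear whether the intervention arm could pass with guideline information.
- *Difficulty in using the aid is itself an outcome being removed.* Section 2 lists only concordance and time.

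**Conclusion.** The point holds in a limited form. The plan puts a selection step that depends on the arm after randomisation, then excludes those who do not get past it, with no count by arm and no rule for their missing answers. Size and direction cannot be derived from the documents. Under the assumed rates in step 2 the planned 30-point difference moves by 2 to 5 points either way. The larger false-positive rates in step 3 need extreme assumptions. If almost everyone passes, or the same share of comparable trainees fails in each arm, the effect on the primary comparison is negligible.

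The timing point is firmer, because it requires no one to be lost: the time the protocol says it captures includes the check, and the secondary outcome does not. Neither part shows that the result would be biased. Both should be corrected because the change is small and, without counts by arm, a reader could not tell whether the check mattered.

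**What to change.** In 3.d, keep the check but make it non-blocking: after a fixed small number of attempts, show the correct answer, record pass or fail, and let the trainee go on to the ten cases. State whether the intervention arm must answer from HIV-ASSIST or may use the guidelines.

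In 3.c and 3.e, include all randomised trainees in the primary comparison by allocated arm, including those who leave at or before this page, and reconcile the one-session exclusion with that. State how missing answers are handled, with a sensitivity analysis that scores trainees with no case answers as not appropriate. Report by arm the numbers randomised, reaching the check, passing it and completing.

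Start the clock for the secondary outcome at case 1.

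The cost is a change to survey branching, a timer at the first case, and a few sentences of text. The downside is that some trainees with a weak grasp of their aid will enter the comparison, which may add variability.

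### The plan records only total survey time, which cannot isolate the time to select a regimen and leaves the secondary comparison open to bias of unknown size and direction

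*Combined protocol and SAP*

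**What the plan says.** **Target.** Section 2 (Objectives), item b, sets the secondary aim: "To determine the difference in time for ARV selection for standardized case scenarios between trainees using HIVASSIST and those using the DHHS guidelines". Item 3.e (Statistical considerations) repeats this, but also frames the outcome differently: "Our secondary outcome will look at the time required for each group to reach a correct answer".

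**Measurement.** Two sentences describe the time data. Item 3.c (Enrollment/Randomization): "The survey will be conducted in one session, and the time to complete the survey will be captured". Item 3.d (Data collection/Survey): "Through Qualtrics software, we will also record the time needed to complete the study". The plan describes no time per case or per page, no start or stop point, and no subtraction of preliminary steps.

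**What else the survey holds.** Under 3.c the survey opens with an explanation and consent page, and the software randomizes participants as part of the survey. Item 3.d adds demographic questions and the following:
- a tutorial: "Each survey will have its own video tutorial briefly explaining how to use the DHHS guidelines and/or HIV-ASSIST", reached from inside the survey ("A link to the video will be provided in the survey");
- resources: "The control group will have a link to the DHHS guidelines in the survey", whereas "The experimental group will have a link to both the DHHS guidelines, and the HIVASSIST tool", and every participant must acknowledge having accessed them;
- an opening question in both surveys that stops progress until it is answered correctly with the arm's aid.

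**The concern.** The quantity of interest is time spent on the ten cases. The quantity recorded, as described, is time spent on the whole survey. If onboarding were the same in both arms, the extra minutes would cancel on average and only add noise. It is not the same: the tutorial, the number of resources and the aid used for the entry question are all set by the assigned arm. Randomization cannot balance steps that are part of the allocation.

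At stake is a hypothesis-tested secondary outcome. A reported difference in time could reflect how long it takes to get started with each aid rather than how long it takes to choose a regimen. Dropping the correct-answer condition in 3.e would not cure this, because onboarding would still sit inside the recorded total. A single total also cannot be split into its parts after data collection.

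**Working it through.** **No figure to reproduce.** The documents give no mean, SD, effect size or power for time, no duration for any onboarding step, and no named test for the time comparison. What can be checked is the structure of the measurement, with illustrations on stated assumptions.

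**Step 1: decomposition.** For each participant, total time = case time + onboarding time + common steps. Consent and demographics are not described as differing by arm, so they cancel in expectation. Taking intervention minus control:

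D_total = D_case + D_onboarding

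The objective concerns D_case. The error from using D_total is exactly D_onboarding, which is zero only if mean onboarding time is equal in the two arms.

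**Step 2: what the documents imply about D_onboarding.** There are reasons for either sign. The intervention arm has two resources to access and control has one, which points to a positive difference. But the Abstract describes the guidelines as hard to work through, and control must pass its entry question using them, which points to a negative one. Neither sign can be derived.

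**Step 3: effect on the estimate.** Assume D_case = -5 minutes, a saving of 5/10 = 0.5 minute per case. Then:

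| Assumed D_onboarding (min) | D_total (min) | Would appear as |
|---|---|---|
| -5 | -5 - 5 = -10 | saving doubled |
| 0 | -5 + 0 = -5 | true saving |
| +5 | -5 + 5 = 0 | no difference |
| +10 | -5 + 10 = +5 | delay |

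In general the saving vanishes when D_onboarding equals its size, and reverses beyond that.

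**Step 4: effect on a test.** Assume case time is truly equal, total time has the same SD in both arms, and onboarding differs by d SDs of total time. For a two-sided 0.05 normal test with n per arm, the chance of a significant result is

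P = 1 - Φ(1.96 - d√(n/2)) + Φ(-1.96 - d√(n/2)).

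Take n = 18, the per-arm size stated for the primary outcome, so √(18/2) = 3. Take also n = 100, half the enrolment ceiling of 200; the 1:1 split is an assumption, since no ratio is stated, and √(100/2) = 7.07.

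| d (SDs) | n = 18 | n = 100 |
|---|---|---|
| 0.1 | 6% | 11% |
| 0.25 | 12% | 42% |
| 0.5 | 32% | 94% |
| 1.0 | 85% | about 100% |

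The nominal rate is 5%. Enrolling more participants does not help: it makes a false finding about case-selection time more likely.

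**The case against.** The strongest reply is that the plan never says when the clock starts. The time sentence in 3.d stands in the item about the ten cases, and 3.e words the outcome as time to selection for those cases, so the investigators may intend to time the cases only. This has some force: inclusion of onboarding is the natural reading of the two time sentences, not an express statement. It does not remove the problem, because both sentences name completion of the survey or study and no case-level measurement is described anywhere.

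A reader might go further and infer that the comparison is biased, and biased against the tool, because intervention participants have a second resource to learn. The documents do not support that. Bias requires mean onboarding times to differ, and no durations are given. Watching the video is not stated to be compulsory, and it is described as brief. Opening a second link need not take minutes. The control arm could be the slower one at the entry question, which would exaggerate a saving.

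It may also be said that onboarding is a real cost of adopting a tool and should be counted. That is a legitimate choice of estimand, but it is not the one the objective states.

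**Conclusion.** The point holds in this form: the stated measurement does not match the stated secondary objective. Following the plan as written yields a total from which case-selection time cannot be recovered, and the between-arm comparison is open to bias through onboarding that is specific to the arm.

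The size and sign of any bias are unknown. The minutes and SD multiples in the working are assumptions chosen to show the range of consequences, not estimates. The conclusion rests on reading survey or study completion time as whole-session time. If the clock was in fact meant to start at the cases, the remedy is the same, because the plan then needs to say so.

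Only the secondary time outcome is affected; the primary concordance comparison is not. The change is worth making before data collection, since it cannot be made afterwards from totals alone.

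**What to change.** 1. In 3.c and 3.d, replace whole-survey time with a time recorded for each case, from display of the case page to submission of its answer. Timing begins after the entry question and is defined identically in both arms. Time spent consulting an aid while a case is open then counts, as it should.
2. In 3.e, define the secondary outcome as total (or mean) case time per participant and name its analysis. Align the wording there, which now moves between time to selection and time to a correct selection. If a correct-answer version is kept, it needs the case-level times; a single clock across all ten cases could not supply it.
3. Report onboarding time (tutorial, resource access, entry question) separately by arm as a descriptive result.
4. If onboarding is meant to count as a cost of the tool, say so in the objective and present that total as a distinct quantity.

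The cost is a few sentences of protocol text and a change to the survey set-up. This assumes that the software can log time by page, which the documents do not state. Participants do nothing extra.
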